8.4.2 RECRUIT

It is proposed that MASCOT will involve a qualitative substudy 'Processes in recruitment to randomised controlled trials (RCTs) of medicines for children (RECRUIT)'. RECRUIT was approved in its own right by the North West REC on 2nd March 2007 (ref 07/MRE08/6).

RECRUIT will be examining communication processes in the recruitment of participants to MASCOT with the aim of identifying strategies for subsequent trials of medicines for children to improve trial recruitment and conduct. RECRUIT will involve:

1. Routine audio-recording of MASCOT discussions (consultations) between families and practitioners (trial recruiters)
2. Follow-up interviews with up to eight families (parents and children, where aged seven or over) who agree to participate in MASCOT
3. Follow-up interviews with up to eight families (parents and children, where aged seven or over) who decline to participate in MASCOT
4. Follow-up interviews with up to eight trial recruiters involved in approaching families to take part in MASCOT

Collection of data for 1 will be facilitated by MASCOT staff who will routinely seek permission to audio-record recruitment consultations from the families whom they approach for MASCOT. Data for 2, 3 and 4 will be collected by the Research Associates (RAs) employed on RECRUIT, who will be entirely independent of MASCOT.

If permission for audio-recording is declined by a family the recruitment consultation will not be recorded. If permission is given the recruiter will activate an audio-recorder. At the end of the MASCOT recruitment consultation the recruiter will discuss RECRUIT with the family and seek their permission to pass their details to one of the RAs employed on RECRUIT, who will then make contact with families and obtain written informed consent for participation in the RECRUIT study. Recordings from families who decline RECRUIT will be erased as soon as practicable. All families who express an interest in RECRUIT but are not selected for follow-up interview will be contacted by letter to thank them and inform them that their recordings have been erased. Audio-recordings of the recruitment consultations will only be released to the RECRUIT RAs after the consent of the participants has been obtained.

All interviews for RECRUIT will be conducted by experienced RAs with proven skills in the conduct of research in sensitive settings. Any distress during the interviews will be managed with care and compassion by the RAs and participants will be free to decline to answer any questions that they do not wish to answer or to stop the interview at any point. The RAs will receive appropriate training and follow a clear protocol for managing participants whose level of distress gives cause for concern. Any such families will be supported in obtaining appropriate help. If necessary, and after discussion with the participant, the lead clinician responsible for the child's care will be informed.

To allow MASCOT to become established and avoid the initial 'teething' phase that most trials experience, sampling for RECRUIT will not begin until the trial has been recruiting for approximately four months. Sampling to RECRUIT (and therefore audio-recording of trial consultations) will roll from trial site to trial site in blocks of up to three months' duration, with planned suspensions if accrual to RECRUIT allows. This will help to minimise the numbers of families who are approached but not selected for RECRUIT. Concentrated sampling at particular sites in time-limited blocks, with the possibility of planned suspensions, will minimise

the impact of RECRUIT on MASCOT and the risk of overburdening particular trial sites. It will also facilitate liaison with the sites and assist recruiters in routine audio-recording of consultations.

8.5 Other Assessments

Childhood asthma represents a significant economic burden to the health service, in terms of treatment and hospital admissions, and to society (the child and their carers) in terms of quality of life; lost schooling and lost time from productive employment (that is time off work caring for a sick child)¹⁴.

An economic analysis will be conducted primarily from a health service perspective but extended to examine a societal perspective by including the child and his/her carer's viewpoint. Both the child and carer's quality of life perspective can be measured using the Paediatric Asthma Quality of Life and Paediatric Asthma Caregivers Quality of Life questionnaires devised by Elizabeth Juniper. Further effects on the carer can be measured by adding additional questions for the carer concerning time lost to paid employment as a result of caring for the child suffering an asthma exacerbation.

The three interventions will be evaluated in terms of their costs and benefits.

Key costs will be use of health service resources; this will include the drugs, visits to general practitioners, home visits from primary health care workers, hospital admissions and A&E attendances. Primary care costs will be a key cost driver in this evaluation. The analysis will be extended to measure costs as they accrue to the patient and their carer. Additional questions will be administered concerning time lost to paid employment due to caring for a child with an asthma related illness. The health economics questionnaire will be lodged in the hand held record at T0, and collected from there at all data collection time points from T+8 to T+48. The data required on resources requires actual recollection of events, so patients and carers will be encouraged to complete the questionnaire on an ongoing basis.

The important measures of outcome will be exacerbations, quality of life, time off school for the child and time off work for parents and carers. The study will seek to measure outcome from both an effectiveness perspective e.g. reduction in exacerbations and reduction in visits to primary care and hospital admissions and from a utility perspective the Juniper measure of quality of life in children. Key outcome measures will be considered alongside the costs.

8.5.1 Health Economics

Health economic data will be collected on primary and secondary health care contacts and medications prescribed. Although not the primary focus of the study, it will aim to incorporate patient and societal costs in terms of time lost to school by the children and time lost to work for the parents and carers. It will include any out of pocket expenses such as personal money spent on medications and aids and appliances. It is important to determine differences in the patient pathway as a result of different regimes.

The four week run-in period can be ignored in terms of the economics as the costs will be common across all patients.

For participants entering the randomised phase, a blank Health Economics (HE) questionnaire will be inserted into their hand held record at each visit for the patient and their carer/s to complete over the following weeks up until their next appointment. This should increase the reliability and accuracy of the data collected by decreasing the family's reliance on retrospective recall of information. The family will receive a telephone call from the RN prior to their visit to remind them to complete and bring along the record and questionnaire for review at their next study appointment. During the visit, the HE questionnaire pages will be removed from the record by the RN. The original will be sent to CTU within seven days and copies made for the Site File and provided to the family (if requested). A new, blank questionnaire will then be inserted into the record for use until the next contact with the study team. At T+24 weeks an extra copy of the HE questionnaire will be inserted into the back of handheld record. At the telephone contact at T+36 weeks, patients/carers will be asked to swap the two questionnaires over and enter the start date on the new questionnaire. At T+48 both questionnaires will be collected from the hand held record.

8.5.2 Quality of Life

The Paediatric Asthma Quality of Life Questionnaire (PAQLQ) should be the first questionnaire completed during the clinic visit and should precede any discussion with the research doctor or nurse. Ideally, children should be interviewed on their own and in a quiet room where there are no distractions. Parents/carers should be instructed to wait in another room if possible, where they can complete the Paediatric Asthma Caregiver's Quality of Life Questionnaire (PACQLQ) while the child completes the PAQLQ. The child should be made to feel comfortable and relaxed but be aware that they need to complete the questionnaire carefully. Where the PAQLQ is interviewer administered (i.e. for children ten years of age and younger) then the questionnaires should be read out exactly as they appear on the form. They should not be reworded or paraphrased for the child, even if they ask for clarification. Children will be asked to base their responses on the past seven days and adults on the previous two weeks.

Two coloured cards (green and blue) will be provided with the PAQLQ, which list sets of response options appropriate to the different questions. The appropriate response card is listed with each question. The interviewer should explain both cards to the child, reading through each of the response options with the younger children and asking the older ones to read each of the responses aloud to ensure they understand them. Children should be reminded that they are only able to choose one option. The PACQLQ is in a self-administered format and carers should be instructed to follow the instructions on the questionnaire.

The research nurse should ensure that all questions have been answered. Once they have collected the completed questionnaires from the participant and their carer, they will make a copy and send the originals to CTU within seven days. The copy will be retained in the Site File. The questionnaires should, wherever possible, only be completed during the study visit. They must always be completed by the same caregiver who completed the first questionnaire and this should be the child's main carer.

8.6 Loss to Follow-up

If any of the trial patients are lost to follow up, contact will initially be attempted through the research nurse and lead investigator at each centre. If the lead investigator at the trial centre is not the patient's usual clinician responsible for their speciality care then follow-up will also be attempted through this latter clinician. Where these attempts are unsuccessful, the child's GP will be asked to contact the family and provide follow-up information to the recruiting centre. This information will be included on the patient information sheet. Wherever possible, information on the reason for loss to follow-up will be recorded.

8.7 Trial Closure

The end of the trial will be considered as the date of the final database lock. However the trial may be closed prematurely by the Trial Steering Committee, on the recommendation of the Independent Data and Safety Monitoring Committee.

9 STATISTICAL CONSIDERATIONS

9.1 Introduction

A separate and full statistical analysis plan (SAP) will be developed prior to the final analysis of the trial. The SAP will be agreed by the trial steering committee before being sent to the independent data and safety monitoring committee for comment and approval. The main features of these planned statistical analyses are included here in the main protocol.

9.2 Method of Randomisation

The randomisation code list will be generated by an MCRN CTU (who is not involved with the MASCOT study) with the software package STATA using block randomisation with variable block length. Randomisation will be stratified by Secondary Care Centre with allocation to the three treatment arms in the ratio of 1:1:1.

9.3 Outcome Measures

9.3.1 Primary

Number of asthma exacerbations requiring treatment with short courses of oral corticosteroids over 48 weeks from date of randomisation.

9.3.2 Secondary

1. Quality of Life as measured by the Paediatric Asthma Quality of Life Questionnaire (PAQLQ) and the Paediatric Asthma Caregivers Quality of Life Questionnaire (PACQLQ)¹³
2. Time from randomisation to first exacerbation requiring treatment with a short course of oral corticosteroids
3. School attendance
4. Hospital admissions
5. Amount of rescue beta₂ agonist therapy prescribed
6. Time from randomisation to treatment withdrawal (due to lack of efficacy or side effects)
7. Lung function at 48 weeks (as assessed by spirometry)
8. Cost effectiveness
9. Adverse events

Thirteen main centres will participate in this study, with an anticipated total accrual for screening of around 75 patients per month across these sites, enabling recruitment of approximately 900 children over 12 months. Assuming either 50% or 75% of children to be eligible for randomisation after the 4 week run-in period would enable either 150 or 225 children to be randomised to each treatment group. The exact percentage of children who will be eligible for randomisation following the 4 week run-in period cannot be estimated yet but will be monitored closely to assess the likely impact on recruitment figures (see interim analysis section).

In summary, our preliminary target number to be randomised is 150 children per treatment group (450 total) with recruitment rates, percentage of children randomised and parameters for sample size calculations closely monitored.

Secondary outcome 'Quality of Life': With 150 children in each group, the power to detect, as significant, a difference of 0.5 points between treatment groups on the Juniper Paediatric Asthma Quality of Life Questionnaire, with assumed standard deviation 0.71¹³ is greater than 99%.

9.5 Interim Monitoring and Analyses

The estimate of overall exacerbation rate (not split by treatment group) and dispersion parameter will be checked after the first 75 children have been randomised and completed their 24 week follow-up assessment. This blinded internal pilot is anticipated to be undertaken at approximately 32 weeks after the first child is randomised. This figure has been chosen to provide adequate data for the sample size review but to ensure that the review is undertaken before the recruitment period ends. This blinded internal pilot will be reviewed by the Independent Data and Safety Monitoring Committee (IDSMC) prior to reviewing any unblinded comparative data. The initial analysis of trial data for IDSMC review is planned at 6 months after the first patient is randomised, to assess recruitment rates (including the percentage of children randomised after the 4 week run-in period) and toxicity.

Subsequent timing of the next analysis of the data will be determined on the basis of recruitment rates at the initial IDSMC meeting although it is anticipated that this will be approximately after a further 6 months. Additional interim analyses may also be triggered by a concern regarding Suspected Unexpected Serious Adverse Reactions (SUSARs).

It is noted that primary outcome data may not be available for the early interim analyses because of the time necessary (48 weeks) to follow-up participants to observe the end point. Any lack of important information will be taken into account by the IDSMC in their monitoring of the trial.

In order to estimate relative treatment effects for the primary efficacy outcome at each interim and final analysis, the Haybittle-Peto approach will be employed for 2 equally spaced interim analyses, planned after 1/3 and 2/3 of the target total number of children have been randomised and followed for 48 weeks, with 99.9% confidence intervals calculated for the difference between each pair of drugs. The final analysis will be undertaken after the final randomised child has completed 48 weeks follow-up and 95% confidence

intervals will be calculated. This method has been chosen to ensure that interim efficacy results would have to be extreme before early termination is recommended in order to be convincing to the clinical community. The method also minimises controversy regarding interpretation of the results from estimation and hypothesis testing at the final analysis. No inflation factor needs to be applied to the sample size using this approach.

All interim analysis results of primary and secondary outcomes will be confidential to the IDSMC members and will not be for review by the trial management group (except the statistical team preparing the IDSMC report). The IDSMC members will make formal recommendations to the trial working group and TSC regarding the continuation of recruitment of patients into the study and will comply with a trial-specific IDSMC charter according to ICH GCP guidelines. The IDSMC may recommend to the TSC that the trial be stopped or amended if sufficient evidence emerges that one treatment is clearly indicated or contra-indicated, as considered by the IDSMC in light of the analyses presented, accounting for other emerging worldwide evidence and overall clinical relevance. The IDSMC will be asked to consider patient safety, particularly any Suspected Unexpected Serious Adverse Reactions (SUSARs) leading to death, alongside treatment efficacy when making their recommendation regarding continuation, amendment or discontinuation of the trial.

9.6 Analysis Plan

The study will be analysed and reported using the 'Consolidated Standard of Reporting Trials' ('CONSORT')^{15,16} and the ICH E9 guidelines.

A full and detailed statistical analysis plan will be written prior to the conduct of the final analysis according to the MCRN CTU Statistical Analysis Plan SOP. To provide a pragmatic comparison of the policies of the different treatments, primary analyses will be performed on an intention to treat basis, analysing all patients according to the treatment group originally allocated. A sensitivity analysis using the per protocol or complier average causal effect (CACE) population as appropriate will be explored to demonstrate robustness of the results. For the overall safety and tolerability assessment, the set of patients to be summarised will be defined as those subjects who received at least one dose of the study drug.

Missing data will be handled by considering the robustness of the complete case analysis to sensitivity analyses using different imputation assumptions informed by data collected on reasons for missing data. Data relating to the primary outcome (oral steroid usage) for those patients who fail to attend for the 48 week assessment visit can be obtained from their GP.

The primary outcome of number of asthma exacerbations requiring treatment with short courses of oral corticosteroids over 48 weeks will be compared between treatment groups using a Poisson regression model (adjusted for centre) with two dummy variables representing 3 treatment groups. Adjustment for overdispersion will be made if appropriate. A secondary analysis adjusting the model for other important prognostic factors (age, sex, duration of asthma, rhinitis, baseline AQLQ, baseline number of courses of oral steroids) will be explored. Statistical tests will be nominally performed at the 1.7% two-sided significance level (with corresponding 98.3% confidence interval), to give a study-wise 5% two-sided significance level (see sample size calculation). The relative exacerbation rate and confidence interval will be calculated for each pair-wise treatment comparison: A compared with B to evaluate the effect of adding in long acting beta₂-agonist (salmeterol 50micrograms twice daily); A compared with C to evaluate the effect of adding in oral leukotriene receptor antagonist (montelukast 5mg once daily); and B compared with C to evaluate the effect of adding in long acting beta₂-agonist (salmeterol 50micrograms twice daily) compared with adding in oral leukotriene receptor antagonist tablet (montelukast 5mg once daily).

For secondary outcomes statistical tests will be performed at the 5% two-sided significance level (with corresponding 95% confidence interval) unless indicated otherwise. Analyses will adjust by centre and secondary analyses adjusting for other important prognostic factors (age, sex, duration of asthma, rhinitis, baseline AQLQ, baseline number of courses of oral steroids) will be explored. For the secondary outcome quality of life, characteristics of responders and non-responders will be compared and potential biases assessed. The score on three domains of activity, symptoms and emotion measured by the Juniper Quality of Life scale, will be assessed over time and treatment groups compared using longitudinal analysis. A joint

modelling approach where time to dropout is taken as the time to event outcome will also be used to explore relationships between dropout and outcome.

Time to first exacerbation requiring treatment with a short course of oral corticosteroids will be calculated for each child and compared across treatment groups using Kaplan-Meier curves and log-rank test with relative effects of treatments summarised using hazard ratios and 95% confidence intervals. The seasonality of having an asthma exacerbation episode will be explored by fitting season as a time-dependent covariate in the model for time to first exacerbation.

Time to withdrawal of randomized treatment will be calculated for each child and compared across treatment groups using Kaplan-Meier curves and log-rank test with relative effects of treatments summarised using hazard ratios and 95% confidence intervals. To examine different reasons for treatment withdrawal (competing risks of unacceptable adverse effects and inadequate asthma control) a cumulative incidence analysis will be undertaken. This approach does not assume competing risks are independent and allows the assessment of cause-specific withdrawal in the presence of other competing risks. All adverse events will be categorised appropriately and the number of patients with occurrences of each event summarised according to treatment group supplemented by calculation of confidence intervals wherever this aids interpretation.

The percentage of school days missed (transformed if appropriate) will be analysed and compared between treatment groups using analysis of variance. The number of hospital admissions will be summarised and compared between treatment groups using bootstrapping techniques which allow comparisons between groups to be based upon the mean difference while making allowance for the non-normal distribution in the calculation of confidence intervals and p-values (Metcalf et al 2003¹⁷). Lung function at 48 weeks will be compared between treatment groups using analysis of covariance (adjusted by baseline lung function). Number of doses of rescue beta₂ agonist therapy prescribed over 48 weeks (transformed if appropriate) will be analysed and compared between treatment groups using analysis of variance. Blinded distribution data will be reviewed and the statistical analysis plan amended accordingly.

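### The primary count model adjusts for centre only and leaves baseline steroid courses to an exploratory analysis, giving up precision if the counts are overdispersed

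*Protocol*

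**What the plan says.** All references are to the protocol.

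- **Stratification (Section 9.2).** "Randomisation will be stratified by Secondary Care Centre", with three arms allocated 1:1:1.
- **Primary outcome (Section 9.6).** Exacerbation counts are compared "using a Poisson regression model (adjusted for centre) with two dummy variables representing 3 treatment groups". On extra variation: "Adjustment for overdispersion will be made if appropriate".
- **Prognostic factors, primary outcome (Section 9.6).** These enter through "A secondary analysis adjusting the model for other important prognostic factors". The list is "age, sex, duration of asthma, rhinitis, baseline AQLQ, baseline number of courses of oral steroids) will be explored".
- **Secondary outcomes, general rule (Section 9.6).** "Analyses will adjust by centre and secondary analyses adjusting for other important prognostic factors" follow the same pattern, with the same list.
- **Secondary outcomes, method by method (Section 9.6).** The two time-to-event outcomes are "compared across treatment groups using Kaplan-Meier curves and log-rank test", with hazard ratios. Rescue beta2-agonist "therapy prescribed over 48 weeks (transformed if appropriate) will be analysed and compared between treatment groups using analysis of variance". School days also get analysis of variance, and admissions a bootstrapped mean difference. Quality of life gets a longitudinal analysis, with no role stated for the T0 score. Lung function is the exception: its analysis of covariance uses the baseline value.
- **Baseline data (Section 8.1).** At T0, exacerbations and beta2-agonist use are reviewed from the hand held record, and both quality-of-life questionnaires are completed.

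**The concern.** A child's earlier count of steroid courses is the baseline counterpart of the primary outcome, and the protocol itself classes it as an important prognostic factor. A covariate of this kind can absorb part of the between-child variation that makes counts overdispersed. With a log link the rate ratio is collapsible, so adding the covariate does not change what is estimated. Section 9.6 nevertheless settles the main model as centre-only and makes the more efficient model exploratory. The same applies to rescue therapy, where baseline use is reviewed but the named analysis has no baseline term.

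There is also a smaller matter of consistency. The general rule promises centre adjustment for secondary outcomes, but the method sentences that follow do not say how it is done. An analyst who took those sentences literally would omit the stratification factor.

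At stake is the width of the confidence intervals and, for the primary outcome, some power at a strict 1.7% level. The validity of the result is not at stake.

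**Working it through.** **Inputs from the protocol.** Section 9.4: rates 1.5 and 1.05 per year (rate ratio 0.7), two-sided level 1.7%, power 80%, loss 10%, 147 per group, target 150, dispersion 0.68. Section 9.3.1: 48 weeks of follow-up. Completers per arm: 150 × 0.9 = 135.

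**Assumed, because the protocol gives no figure.** Dispersion φ from 1 to 2; share R² of the extra-Poisson variance explained by baseline from 0.1 to 0.5.

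**1. The protocol's own figure.** With t = 1 year, n = (1/1.5) × (1 + 1/0.7) × (2.387 + 0.842)² / (ln 0.7)² = 132.6, and 132.6/0.9 = 147.4. The stated 147 reproduces. With t = 48/52 the formula gives 143.7, or 159.7 after loss. That is a separate matter, but 48/52 is used below because it is the follow-up analysed.

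**2. Power with centre only.** Expected events are 1.5 × 135 × 48/52 = 186.9 and 1.05 × 135 × 48/52 = 130.8. SE of the log rate ratio = √[φ(1/186.9 + 1/130.8)] = 0.1140√φ. Power = Φ(0.3567/SE − 2.387). At φ = 1.5, SE = 0.1396 and power = 56.7%.

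**3. Power with baseline added.** φ_adj = 1 + (φ − 1)(1 − R²), put into the same formula:

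| φ | Centre only | R² = 0.1 | R² = 0.3 | R² = 0.5 |
|---|---|---|---|---|
| 1 | 77% | 77% | 77% | 77% |
| 1.25 | 66% | 67% | 69% | 71% |
| 1.5 | 57% | 58% | 62% | 66% |
| 2 | 43% | 45% | 51% | 57% |

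At φ = 1.5 the variance falls by 3.3%, 10% and 16.7% across the three R² columns.

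**4. Check by simulation.** Quasi-Poisson fits, 13 centres, 150 per arm, one year, 600 runs.

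- No heterogeneity: mean SE 0.104 with or without the covariate.
- Assumed log-scale SDs of 0.2 (centre), 0.3 (baseline) and 0.4 (residual): SE goes from 0.121 to 0.115 and power from about 73% to 78%.
- Baseline SD raised to 0.5: SE goes from 0.131 to 0.115 and power from about 66% to 78%.

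The simulated covariate was measured without error and linear on the log scale, which favours adjustment.

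**5. Is overdispersion plausible?** The 0.68 comes from children selected for at least one course in the previous 12 months. If the counts cover that same period, zeros are excluded. A zero-truncated Poisson with mean 1.5 solves λ/(1 − e^−λ) = 1.5, so λ = 0.874, and its variance is 1.5 × (1 + 0.874) − 1.5² = 0.561. The quoted variance of 1.02 is 1.8 times that. Entry to MASCOT does not require a previous course (Sections 5.1.1 and 5.2.1), so zeros will occur.

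**6. Quality of life.** SE = 0.71 × √(2/150) = 0.0820 and 0.5/0.0820 = 6.10, so power is 99.998%, in line with the protocol's statement of more than 99%. The difference detectable with 80% power is 2.80 × 0.0820 = 0.230. With an assumed baseline correlation of 0.3, 0.5 or 0.7, multiplying by √(1 − r²) gives 0.219, 0.199 or 0.164. This compares analysis of covariance with a single unadjusted follow-up score, so it does not measure the gain over a longitudinal model that may already use T0.

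**7. Centre.** A centre-stratified log-rank test and a centre-stratified Cox model both ran without difficulty on simulated data of this shape. Analysis of variance can take centre as a factor, and a bootstrap can be resampled within centre.

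**The case against.** The strongest reply has four parts.

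- **The primary analysis is sound and the adjusted model is already planned.** This stands. The model contains the only stratification factor, and the proposal changes which analysis leads.
- **On the protocol's dispersion of 0.68 there is nothing for a covariate to remove.** This stands as arithmetic: the gain at dispersion 1 is nil. It is weakened by where 0.68 comes from (step 5), by Section 9.4's own caution that the source may not represent the randomised children, and by the provision for overdispersion in Section 9.6.
- **This is detail for the SAP.** It stands for the role of the T0 score and the exact form of the secondary tests. It does not stand for the primary covariates, which Section 9.6 settles.
- **Baseline rescue use and the rescue outcome are different measures.** This stands. One is recorded use, the other prescribed doses, so the covariate may predict less well than a like-for-like baseline.

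Two stronger readings are tempting. A reader might infer that the named secondary tests are unable to adjust for centre. They are not: each has a centre-adjusted form, and the general rule in Section 9.6 already calls for it. A reader might also infer that main analyses ignore baseline values throughout. Lung function uses its baseline, and the longitudinal quality-of-life analysis is silent on T0 rather than excluding it.

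**Conclusion.** The point holds as one of efficiency. Section 9.6 relegates an available, protocol-listed predictor of the primary outcome to an exploratory analysis and names no baseline for rescue therapy. At an assumed dispersion of 1.5, adjustment would raise power from about 57% to between 58% and 66%. The upper end requires baseline to explain half of the extra-Poisson variance; at 10% explained the gain is under 2 points, and at dispersion 1 it is zero. The low starting value of 57% comes mainly from the assumed dispersion, since the same calculation gives 77% at dispersion 1, and should not be charged to the missing covariate. For quality of life the benefit is narrower intervals only.

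The documents do not show that precision is in fact lost, because that depends on dispersion and on an association they do not report. On centre, the rule is stated and can be carried out; what is needed is method wording that matches it.

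**What to change.** - **Primary outcome:** prespecify centre and baseline number of steroid courses as covariates in the main count model, and define the look-back period for the baseline count, which Section 9.6 does not give. Keep the centre-only model as a sensitivity analysis.
- **Quality of life:** include the T0 PAQLQ or PACQLQ score in the corresponding main longitudinal model.
- **Rescue therapy:** add baseline beta2-agonist use as a covariate, noting that it records use and not prescribed doses.
- **Centre:** state the secondary methods in the form the general rule implies: stratified log-rank and Cox for the time-to-event outcomes, centre as a factor in the analyses of variance, and resampling within centre and arm for admissions.

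The cost is minor SAP wording, with Section 9.6 brought into line, and a stated rule for missing baseline values. No extra children or visits are needed. The choice should be made before any unblinded comparison is seen.
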